#### **5.4 Assessing Severity**

The safety concepts of "severity" and "seriousness" are distinct concepts (see Section 5.8). Severity refers to a degree of clinical manifestation. "Seriousness" refers to defined outcomes from an adverse event. A severe adverse event is not always serious and a serious adverse event is not always severe.

For all adverse events, the investigator (or designee, who is a healthcare professional; is someone the investigator deems qualified to review adverse event information, to provide a medical evaluation of the event, and to classify the event based upon medical judgment and the severity

categories described below) is responsible for assessing the severity of the event and the causal relationship of the event to the study drug.

The **severity** of all adverse events, including clinical findings and abnormal laboratory values, will be classified as one of the following grades:

1. **Mild**
2. **Moderate**
3. **Severe**

A Toxicity Table is provided in the protocol appendices for the assessment of severity of specified adverse events. The Toxicity Table Adverse Event Grades do not correlate directly with the classical severity grades of mild, moderate and severe. FOR THE PURPOSES OF RECORDING EVENTS ON THE CRF, Toxicity Table Grade 1 events will be considered mild in severity, Toxicity Table Grade 2 events will be considered moderate in severity, and both Toxicity Table Grade 3 and 4 events will be considered as severe. In the Toxicity Table certain local reactions such as erythema (redness) and swelling are graded according to size. Laboratory values are graded according to level of deviation from the normal range.

For adverse events not listed in the Toxicity Table determination of severity requires some level of interpretation as outlined below. The degree of incapacity caused by the adverse event and the level of medical intervention required for treatment may be helpful in assessing the overall severity of the adverse event.

For example:

- “Mild” events are generally regarded as noticeable but have no impact on normal activities; they may or may not require over-the-counter treatment managed by the subject.
- “Moderate” events generally have some impact on an individual’s normal activities and may require general symptomatic medical intervention by a healthcare professional or by the subject.
- “Severe” adverse events may be incapacitating, leading to suspension of normal daily activities, and would generally require more immediate medical evaluation and intervention by a healthcare professional.

A change in severity of an adverse event will not be recorded as a new adverse event. Only the highest severity level that occurs during the entire period of the adverse event will be recorded on the CRF with the onset and resolution dates encompassing the entire duration of the event.

## **5.5 Assessing Causal Relationship (Relatedness)**

For all adverse events, the investigator and the sponsor (the medical monitor) will determine a **causal relationship**, to the study drug without knowledge, for the blinded principal investigator, of whether SYN023, placebo, or active control was administered. Serious Adverse Events considered related to other medicinal products administered during the trial such as RIG or the rabies vaccine may occur and are subject to reporting to the manufacturer who will have a post-marketing reporting obligation to the FDA if the event is unexpected. A number of factors will be considered in making this assessment, including: 1) the temporal relationship of the event to

the administration of the study drug 2) whether an alternative etiology has been identified and 3) biological plausibility. The investigator will use the following guidelines to assess the causal relationship of an adverse event to study drug:

- **Not Related** to study drug (i.e., there is no evidence of a causal relationship; another etiology is known to have caused the adverse event. The alternative etiology should be documented in the subject's study record).
- **Unlikely Related** to study drug (i.e., there is less than a reasonable possibility that the adverse event was caused by study drug).
- **Possible** relationship to study drug (i.e., there is a reasonable possibility that the adverse event was caused by study drug. There must be a plausible mechanism for the event to be related to study drug. The evidence is inadequate to accept or reject, or favors rejection of, a causal relationship; an association exists between the event and the study drug but there may also be an alternative etiology, such as characteristics of the subject's clinical status or underlying condition).
- **Probable** relationship to study drug (i.e., it is likely that the adverse event was caused by administration of the study drug. The evidence favors acceptance of a causal relationship; an association exists between the event and receipt of the study drug and there is a plausible mechanism for the event to be related to the study drug, and an alternative etiology is not apparent).
- **Definite** relationship to study drug (i.e., the study drug is known to be the cause of the adverse event. The evidence establishes a causal relationship; an association exists between the event and receipt of the study drug and there is a plausible mechanism for the event to be related to the study drug, and causes other than the study drug have been ruled out).

The principal investigator and the local medical monitor both determine causality. It is expected that communication and consultation may occur in the assessment of the causality of adverse events. The greatest degree of causal relationship (definite > probable > possible > unlikely related > not related) determined by either the investigator or local medical monitor after their discussions will determine the ultimate classification of the adverse event. Definite, probable and possible are considered to be related. Not related and unlikely related are considered to be unrelated.

Every effort should be made by the investigator to determine the existence of any pre-existing conditions (e.g., headache in adults or rashes in infants on Study Day 0 with onset prior to study vaccination) that must be taken into consideration when assessing causal relationship of an adverse event. Pre-existing conditions should be recorded in the CRF as baseline history and substantiated by appropriate source documentation. Intermittent conditions such as headaches in adults or irritability in infants may not be present on Study Day 0 but may represent an adverse event if the intensity or duration of the event is worse than usual following study drug.

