## **3.4 Blinding**

Because of different volumes for RIG and SYN023 this study is incompletely blinded. In a strict sense it is a single blind study since the subject will not be told which treatment he or she is receiving. The sponsor and the medical monitor are unblinded. The statistician is unblinded.

The other unblinded persons on the study are the study drug manager or pharmacist (and designee, if appointed) and the study monitor(s). All unblinded persons must take care to not reveal individual subject treatment regimen assignments to any other member of the study team. The subject, the principal investigator and most of the study team remain blinded to reduce bias in safety assessment.

The study drug manager or pharmacist (and designee) must have no other clinical or regulatory responsibilities associated with the conduct of the study during the entire study period. With the exception of the medical monitor, unblinded study personnel must not participate in the evaluation of adverse events. A Delegation of Authority Log will be maintained by the site and will identify the individual(s) authorized to function as the study drug manager, i.e., individuals with access to study blinding information.

The randomization schedule will be provided by the unblinded statistician to the study drug manager in a sealed tamper-evident envelope. Access to the randomization schedule during the study will be provided only to the study drug manager (or designee in the pharmacy), the study monitor, and the sponsor's investigational product manager (and/or designee). The randomization schedule and all pharmacy source documents and dose preparation records that can link a subject identification number with a treatment assignment must remain secure (e.g., in the pharmacy with access limited to only unblinded persons) until notification from the sponsor that the study has been unblinded.

Labels accompanying the syringes of prepared study drug doses will not indicate which vaccine is in the syringe. Identical syringes and needles will be used for preparation and administration of each study drug.

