#### **5.1.3 Medical Monitor**

The local medical monitor is the sponsor's representative and is a licensed physician or surgeon in their country of residence. The local medical monitor reviews the safety of the product for protocols in a specific region and determines expectedness of the adverse event. The local medical monitor may make a sponsor's assessment of severity and causality for adverse events that may upgrade the degree of severity and causality determined by the principal investigator. The local medical monitor, unlike the principal investigator, is unblinded for the study.

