## **5.6 Definition of Adverse Reaction**

An adverse reaction is an adverse event judged to be related to study drug (see Section 5.3 for adverse event definition).

**Related adverse events (adverse reactions) are defined as those judged by the investigator or local medical monitor to be possibly, probably, or definitely related to study drug.**

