9.2.2 Unsolicited Adverse Events

Unsolicited AEs are any unsolicited unfavorable or unintended sign, symptom, disease, syndrome, abnormal laboratory finding, or concurrent illness that emerges or worsens after receipt of study vaccine relative to the subject's pre-treatment baseline, whether or not it is considered to be related to the medicinal product. The unsolicited AE reporting period begins with the day of vaccination (Day 0) through Day 42 inclusively. Additionally, any solicited AE (local or systemic) that persist beyond Day 28 will be recorded as an unsolicited AE.

Summary of descriptive statistics for unsolicited AEs (incidence of subjects with percentages and incidence of unsolicited AEs) will be presented by treatment and overall, SOC, PT, by investigator-assessed relationship (Not Related, Unlikely Related, Possible, Probable, and Definite) and severity (Mild, Moderate, and Severe). For incidence of subject calculations, each subject may only contribute once to each of the incidence rates, for an unsolicited AE following a given treatment, regardless of the number of occurrences; the highest severity or highest relationship will be presented, as appropriate.

In each table, SOC will be presented in descending order of overall incidence rate in terms of frequency of subjects and then in frequency of events (alphabetical order will be used in case of equal rates). For each SOC, PT will be presented the same way.

All unsolicited AEs will be listed.

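### An unblinded medical monitor can set final relatedness, seriousness and upgraded severity, and the SAP does not say its investigator-assessed tables use the rating made before discussion with that monitor

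*Protocol*

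**What the plan says.** **Who knows the arm.** Protocol 3.4: "The sponsor and the medical monitor are unblinded". Protocol 5.1.3: "The local medical monitor, unlike the principal investigator, is unblinded for the study". Section 3.4 gives reduction of bias in the safety assessment as the reason for keeping the investigator and most of the team blinded, and it tells unblinded persons not to reveal assignments. It then makes one exception: "With the exception of the medical monitor, unblinded study personnel must not participate in the evaluation of adverse events".

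**What the monitor can do.** Under Protocol 5.1.3 the monitor's assessment "may upgrade the degree of severity and causality determined by the principal investigator". Under Protocol 5.5 both the investigator and the monitor determine causality, and "It is expected that communication and consultation may occur in the assessment of the causality of adverse events". The greatest degree of relationship "determined by either the investigator or local medical monitor after their discussions will determine the ultimate classification of the adverse event". Protocol 5.6 defines related events as those "judged by the investigator or local medical monitor to be possibly, probably, or definitely related to study drug". Protocol 5.8 treats seriousness the same way: either assessor is enough.

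**What is tabulated.** SAP 9.2.1 (solicited) and 9.2.2 (unsolicited) present AEs by treatment, "by investigator-assessed relationship (Not Related, Unlikely Related, Possible, Probable, and Definite"), and by severity. SAP 9.2.3 lists SAEs. Protocol 7.6.1 counts each subject once per preferred term at the worst severity or most related state on record, without naming an assessor.

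**The concern.** Comparing safety with RIG or SYN023 is the first-listed secondary objective. The protocol blinds the investigator to protect that comparison, then allows an arm-aware sponsor representative to discuss causality before it is settled and to raise the result.

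The documents attach different consequences to the same event in the two arms. The SUSAR definition in Protocol 5.10 concerns an investigational product such as SYN023. The stopping rules in 6.2 turn on relation to SYN023. Under 5.5, serious events attributed to RIG or vaccine go to the manufacturer. A different threshold by arm is therefore plausible, in either direction, although nothing shows that it would occur.

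Safety is summarized without inferential analysis (SAP 9), so readers will take the by-arm percentages at face value. If the investigator's pre-discussion rating is not kept, arm-dependent attribution could not be detected afterwards.

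**Working it through.** The plan states no figure on this point, so there is nothing to reproduce. The check sets the sections side by side, then shows how the either-assessor rule behaves under assumed values.

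**1. Routes by which arm knowledge can enter**

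| Item | Formal route | Informal route | Reaches a planned SAP output? |
|---|---|---|---|
| Causality | Higher call is final (Protocol 5.5, 5.6) | Discussion before the call is settled (5.5) | Formal route: not on the SAP's wording, which uses the investigator's rating. Informal route: yes, if that rating is made or changed after discussion |
| Severity | Monitor may upgrade (5.1.3) | None stated; the consultation sentence in 5.5 concerns causality | Unclear: the SAP can be read as using the investigator's grade but does not settle it |
| Seriousness | Either assessor is enough (5.8) | None stated | Yes, through which events enter the SAE listing (SAP 9.2.3) |

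**2. What is not exposed to the causality call**

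- The primary safety variable in Protocol 7.6.1 is the number and percentage of AEs. It needs no relatedness judgement.
- Protocol 5.7 fixes injection-site pain, redness and swelling as related, and also ulceration, scarring and regional lymphadenopathy. Their causality is set by rule in both arms, although their severity is still graded.
- Other systemic solicited events and other unsolicited events do need a causality judgement.

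**3. Which classification feeds the tables**

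Protocol 5.6 defines a related event by either assessor, whereas SAP 9.2.1 and 9.2.2 use the investigator alone. SAP 4, which lists changes from the protocol, covers only the pharmacodynamic parameters. Neither document says whether the investigator's rating is fixed before discussion.

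**4. Illustration of the higher-call rule (assumed values only)**

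Let p be the share of events that the blinded investigator calls related, and u the probability that the monitor upgrades an event the investigator called unrelated. Then

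final related share = p + (1 − p) × u

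With the same p in both arms, the spurious difference is (1 − p) × (u for SYN023 − u for RIG).

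| p | u, RIG | u, SYN023 | Final share, RIG | Final share, SYN023 | Difference |
|---|---|---|---|---|---|
| 0.30 | 0.05 | 0.05 | 0.335 | 0.335 | 0 |
| 0.50 | 0 | 0.05 | 0.500 | 0.525 | 2.5 points |
| 0.30 | 0 | 0.10 | 0.300 | 0.370 | 7 points |
| 0.30 | 0.05 | 0.20 | 0.335 | 0.440 | 10.5 points |
| 0.10 | 0 | 0.20 | 0.100 | 0.280 | 18 points |

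Neither p nor u is anchored in the documents. The formula describes the protocol's final classification, which the SAP does not tabulate. It shows only that equal upgrading produces no difference and unequal upgrading does.

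**The case against.** The best defence is that the arrangement is deliberate, disclosed and protective. Protocol 3.4 admits incomplete blinding and exempts the monitor by name. The monitor's formal power is to upgrade only, so it cannot lower a SYN023 attribution. Taking the higher call is cautious for pausing and reporting. This stands, and the fix leaves it alone.

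Second, the SAP uses the investigator's rating, the investigator must judge causality without knowing the arm (Protocol 5.5), and assignments must not be disclosed (3.4). This narrows the concern to informal influence on relatedness, but does not close it. An opinion can be informed by the arm without revealing it, and discussion, unlike the formal power, can move a rating down as well as up.

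Third, severity is primarily the investigator's task (5.4), many grades follow toxicity-table cut-offs, and the SAP wording can be read as investigator-assessed for both relationship and severity. That reading is reasonable. The SAP should state it, because 5.1.3 allows an upgrade.

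Fourth, a reader might infer that no clean blinded rating will be kept. The documents do not show this. The CRF layout is not among them, and nothing says that the monitor's call overwrites the investigator's. What can be said is that neither document requires the pre-discussion rating to be kept or used.

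**Conclusion.** The point holds as a gap in the relatedness, severity and seriousness breakdowns, all of them descriptive. An unblinded monitor can set final relatedness and seriousness and can raise severity. The blinded investigator's causality rating may be made or changed after discussion with that monitor. The SAP neither says which rating it tabulates nor reconciles its tables with the protocol's definition of a related event.

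A reader might go further and infer that the whole RIG-versus-SYN023 harm comparison rests on arm-aware judgements. The documents do not support that. AE incidence needs no causality call, several local events are related by rule, the relationship tables use the investigator's rating, and consultation is something that may happen, not a required step.

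The size of any bias cannot be derived from the documents. It is zero if the monitor acts equally in both arms. The non-zero differences in the illustration depend wholly on assumed values and should not be quoted as estimates. The change is worth making because it is cheap and removes a route for bias that the plan leaves open.

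**What to change.** **Protocol 5.5.** Require the blinded investigator's severity and causality to be entered in the CRF before any discussion with the medical monitor, and not overwritten. Record the monitor's assessment in a separate field.

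**SAP 9.2.1 and 9.2.2.** State that the by-arm relatedness and severity tables use the pre-discussion blinded entry. Add a separate table of the either-assessor final classification, with the monitor's upgrades by arm, and explain how it relates to the definition in Protocol 5.6.

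**Unchanged.** Safety reporting and the pausing rules continue to use the final classification.

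**Cost.** A short protocol addition, separate CRF fields for the two assessments and an extra table, with no additional staff. The downside is that two classifications appear in the report and need a line of explanation.

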## **5.6 Definition of Adverse Reaction**

An adverse reaction is an adverse event judged to be related to study drug (see Section 5.3 for adverse event definition).

**Related adverse events (adverse reactions) are defined as those judged by the investigator or local medical monitor to be possibly, probably, or definitely related to study drug.**

## **5.7 Solicited Adverse Events and Injection Site Reactions**

Solicited adverse events are events the subject is specifically asked about. These adverse events are commonly observed soon after receipt of study antibody. For this study, solicited adverse events to be collected include: to be collected include the following: injection site (s) pain, tenderness, redness swelling, warmth, skin disruption and regional lymphadenopathy. Non-local solicited symptoms include headache, arthralgia, myalgia, rash, pruritus, urticaria, dyspnea, chest pain, cough, fever and chills. Solicited adverse events of local injection site reactions (i.e., pain at injection site, redness at injection site, or swelling at injection site will be considered causally related to study drug (adverse reaction).

**The reporting period during which *solicited* adverse events will be evaluated is specified in Table 3.1-1.** The solicited adverse event reporting period begins with the day of vaccination. Adverse events and solicited adverse events including assessment of local injection site reactions will be assessed by the investigator for severity, causal relationship to the study drug, possible etiologies, and whether the event meets criteria as a serious adverse event (and therefore requires immediate notification to the medical monitor).

Presence of ulceration and/or scarring at the site of injection and axillary lymphadenopathy of the injection arm(s) in adults or localized lymphadenopathy (e.g., groin) of the thigh injections are considered to be adverse events that are causally related to the study drug and are of special interest. Site of injection ulceration (including presence of drainage) and axillary lymphadenopathy will be actively evaluated during each clinic visit through study day 28. These events will be recorded on the Adverse Event CRF.

In the event that the clinical presentation meets the definition of a serious adverse event, an SAER form must be completed and the event reported per protocol instructions.

## 5.8 Assessing “Seriousness” and Serious Adverse Events

Seriousness refers to the outcome of an adverse event. Seriousness is determined by both the principal investigator and the local medical monitor. If either principal investigator or local medical monitor determines an event to be serious, it will be classified as such. If any of the following outcomes are present then the adverse event is serious:

- It results in **death** (i.e., the AE caused or led to the fatality). Serious does not describe an event which hypothetically might have caused death if it were more severe.
- It was immediately **life-threatening** (i.e., the AE placed the subject at immediate risk of dying. It does not refer to an event which hypothetically may have led to death if it were more severe).
- It required inpatient **hospitalization** or prolonged hospitalization beyond the expected length of stay. Hospitalizations for scheduled treatments and elective medical/surgical procedures related to a pre-existing condition that did not increase in severity or frequency following receipt of study drug, are **not** serious by this criterion. Hospitalization is defined as a hospital admission or an emergency room visit for a period greater than 24 hours.
- It resulted in a persistent or significant **disability/incapacity** (i.e., substantial reduction of the subject’s ability to carry out activities of daily living).
- It resulted in a **congenital anomaly or birth defect** (i.e., an adverse finding in a child or fetus of a subject exposed to the study drug prior to conception or during pregnancy).
- Other **medically important conditions** that may not result in death, threaten life or require hospitalization (i.e., the AE does not meet any of the above serious criteria) may be considered a serious adverse event when, based on appropriate medical judgment, they may jeopardize the subject and require medical or surgical intervention to prevent one of the serious outcomes listed in these criteria (e.g., allergic bronchospasm requiring intensive treatment in an emergency room or at home; blood dyscrasias or convulsions that do not result in hospitalization, or the development of drug dependency or drug abuse).

A **serious adverse event** is an adverse event meeting the outcome criteria for seriousness regardless of relationship to an administered medicinal product.

